5.1.1 Tremelimumab and MEDI4736(durvalumab)

1.1.1.1 Regimen Description					
Agent	Premedication; Precautions	Dose	Route	Schedule	Cycle Length
Tremelimumab	Mot routinely	75mg	IV over 1 hour before	Day 1	28 days

	necessary unless prior infusion reaction	Max of 4 doses	MEDI4736/durvalumab; refer to section 8.1.2 for compatible infusion set materials		(4 weeks)
MEDI4736(durvalumab)	Not routinely necessary unless prior infusion reaction	1500mg Max of 13 doses	IV over 1 hour; refer to section 8.1.1 for compatible infusion set materials	Day 1	

Patients will receive tremelimumab 75 mg q4w for 4 doses in combination with MEDI4736, 1500 mg for 4 doses, followed by MEDI4736monotherapy 1500 mg q4w initiated 4 weeks after the last combined dose and administered for up to 9 additional doses. Observation period for post MEDI4736 will be 60 minutes.
 
MEDI4736 infusion will start approximately 1 hour after the end of tremelimumab infusion for the first infusion only. Infusions may be administered consecutively at subsequent infusions at the Investigator's discretion.
 
A window of +/-10 minutes is allowed for infusion of study treatment.
 
A window of +/- 2 days is allowed between cycles.
					

5.1.2 Radiation therapy

The individual medical / radiation oncologist may deliver supportive care as indicated. The use of prophylactic steroids before or after the radiation treatments is not allowed. In patients who receive radiation twice per day, at least 6 hours must elapse between treatments.

5.2 Definition of Dose-Limiting Toxicity

Although there is significant safety data for the MEDI4736/ tremelimumab treatment and palliative radiation, the combination is relatively untested, although emerging safety data suggests the combination of the two treatments (specifically in regards to limited palliative radiation treatment fields) do not increase the rates of irAE or radiation toxicity [64]. Although this retrospective data compares favorably to previous studies testing combined checkpoint inhibition, to provide greater confidence in the safety of radiation and combined checkpoint inhibition, DLT's will be monitored in a step-wise fashion and over time. As part of the safety assessment for the NSCLC cohort, complete review of the adverse event data for the first 10 patients assigned to MEDI4736(durvalumab)/tremelimumab/high-dose RT and for the first 10 patients assigned to treatment with MEDI4736(durvalumab)/tremelimumab/low-dose RT will occur after completion of two cycles of therapy. If three or more patients within a therapy arm experience one or more pre-specified dose-limiting toxicities the addition of RT will be considered too toxic and enrollment to that arm will stop. If this occurs in the high-dose radiation arm, all safety data from that arm will be reviewed and a protocol amendment may be considered.

Concurrent with the end of the first stage of each Simon design for the colorectal cohort, a complete safety review of adverse event data will be conducted for each treatment. If three of more patients within a therapy experience one or more pre-specified dose-limiting toxicities, enrollment to that arm will stop.

Dose-limiting toxicity (DLT) is based on the CTEP Active Version of the NCI Common Terminology Criteria for Adverse Events (CTCAE). Although we will continue to monitor toxicity over time, the DLT period in this study refers to toxicities experienced during the first 4 weeks of treatment.

DLTs will be graded according to the National Cancer Institute's CTCAE v5.0 https://ctep.cancer.gov/protocolDevelopment/electronic_applications/ctc.htm (<http://ctep.cancer.gov/forms/CTCAEv45.pdf>).

A DLT will be defined as any <<Grade 3 or higher>> toxicity that occurs during the DLT evaluation period. Toxicity that is clearly and directly related to the primary disease or to another etiology is excluded from this definition. The following will be DLTs:

- Any Grade 4 irAE
- Any \geq Grade 3 colitis
- Any Grade 3 or 4 noninfectious pneumonitis irrespective of duration
- Any Grade 2 pneumonitis that does not resolve to \leq Grade 1 within 3 days of the initiation of maximal supportive care
- Any Grade 3 irAE, excluding colitis or pneumonitis, that does not downgrade to Grade 2 within 3 days after onset of the event despite optimal medical management including systemic corticosteroids or does not downgrade to \leq Grade 1 or baseline within 14 days
- Liver transaminase elevation $> 8 \times$ ULN or total bilirubin $> 5 \times$ ULN
- Any grade 3 or 4 febrile neutropenia
- Any grade 3 or 4 thrombocytopenia with significant bleeding
- Any \geq Grade 3 non-irAE, except for the exclusions listed below

The definition excludes the following conditions:

- Grade 3 fatigue lasting ≤ 7 days
- Grade 3 endocrine disorder (thyroid, pituitary, and/or adrenal insufficiency) that is managed with or without systemic corticosteroid therapy and/or hormone replacement therapy and the subject is asymptomatic
- Grade 3 inflammatory reaction attributed to a local antitumor response (eg, inflammatory reaction at sites of metastatic disease, lymph nodes, etc)
- Concurrent vitiligo or alopecia of any AE grade

- Grade 3 infusion-related reaction (first occurrence and in the absence of steroid prophylaxis) that resolves within 6 hours with appropriate clinical management
- Grade 3 or 4 neutropenia that is not associated with fever or systemic infection that improves by at least 1 grade within 3 days. Grade 3 or Grade 4 febrile neutropenia will be a DLT regardless of duration or reversibility
- Grade 3 or 4 lymphopenia
- Grade 3 thrombocytopenia that is not associated with clinically significant bleeding that requires medical intervention, and improves by at least 1 grade within 3 days
- Isolated Grade 3 electrolyte abnormalities that are not associated with clinical signs or symptoms and are reversed with appropriate maximal medical intervention within 3 days
- Grade 3 fever lasting \leq 24 hours with or without medical therapy and is not considered an SAE

Immune-related AEs (irAEs) are defined as AEs of immune nature (i.e., inflammatory) in the absence of a clear alternative etiology. In the absence of clinical abnormality, repeat laboratory testing will be conducted to confirm significant laboratory findings prior to designation as a DLT.

While rules for adjudicating DLTs are specified above, an AE that is Grade $<$ 3 or listed as exempt above may also be defined as a DLT after consultation with the sponsor and Investigators, based on the emerging safety profiles of MEDI4736 and tremelimumab. Likewise, subjects who become not evaluable for DLT because they discontinued or interrupted treatment due to toxicities other than DLTs will be counted as DLT subjects using the same criteria as other DLTs (Grade 3 or higher toxicity that occurs during the DLT evaluation period and excluding toxicity that is clearly and directly related to the primary disease or to another etiology.)

Management and dose modifications associated with the above adverse events are outlined in Section 6.

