- 3) Prescriptions: Patients randomized to higher dose radiation arm (Arm A) will be prescribed a total dose of 24 Gy in 3 fractions. Patients randomized to the lower dose radiation (Arm B) will be prescribed a total dose of 2 Gy in 4 fractions to be repeated with each of the first 4 cycles (total overall dose 8 Gy). In cohort 1 (NSCLC), patients randomized to the no radiation arm (Arm C) will not receive any radiation. Please also

refer to schema below:

NSCLC Cohort- Cohort 1

Colorectal Cohort- Cohort 2

*0.5 Gy BID x2 days repeated q4weeks with durvalumab / tremelimumab

Only photons treatments are allowed, and volumetric treatment planning is mandated. Planning may be 3D conformal, IMRT or SBRT, as appropriate to each individual case / lesion to achieve coverage of the PTV target and maintain normal tissue tolerance. The percentage PTV covered to 100% of the prescription dose will be reported along with the maximum hotspot; reasonable effort should be made to keep this greater than 95% while maintaining normal tissue dose constraints as indicated below. Bolus may be used as appropriate. Note that for patients prescribed 24 Gy in 3 fractions, maximum hotspot should not exceed 115% in any case.

- 4) Timing of radiation treatment:
- Arm A: Higher dose radiation. Radiation will start on week 2. Three treatments of 8 Gy will generally be delivered every other day. They must not be delivered on consecutive calendar days and more than one fraction may not be delivered on the same day. The total treatment time must not extend over more than 10 calendar days. Shorter treatment courses (approximately 5 days) are favored, but no specific

treatment schedule is mandated to account for weekends, holidays, machine maintenance, etc.

- Arm B: Lower dose radiation: Radiation will start on week 2. Four treatments of 0.5 Gy will be delivered no more frequently than every 6 hours and will be scheduled to occur twice per day over a period of two days. Although treatment is allowed to extend over three calendar days in the case of machine maintenance or patient illness, this is strongly discouraged.

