 - o Note: Patients enrolled on Arm B should continue to receive lower dose radiation (2 Gy delivered in 4 fractions) with each of the first 4 cycles of treatment (weeks 2, 6, 10, 14). The radiation target and treatment plan need not change between treatment courses; however, if there is clinical or radiographic evidence of complete resolution of the irradiated lesion, this lesion should not be treated with additional radiation. If this occurs and there is another lesion appropriate for palliative radiation that satisfies the above criteria, additional lower dose radiation may be considered after discussion with the study PI. This irradiation of a new lesion will not be counted as tumor progression.

5) Dosimetry:

- a. Only photons treatments are allowed, and volumetric treatment planning is mandated.
- b. Planning may include 3D conformal, IMRT or SBRT, as appropriate to each individual case / lesion to achieve coverage of the PTV target and maintain normal tissue tolerance. IROC credentialing is required for the most complex modality (IMRT>3D) used by each center as well as for IGRT (see section 4.2.2).
- c. PTV coverage should ideally be 95% of PTV conformally covered by the prescription isodose surface (D95=100%), , while maintaining normal tissue dose constraints as indicated below. Bolus may be used as appropriate
- d. The percentage PTV covered to 100% of the prescription dose will be reported along with the maximum hotspot;
- e. Doses higher than the prescription isodose (i.e., hotspots) should be manipulated to occur within the planning target volume.
- f. Note:For patients prescribed 24 Gy in 3 fractions, maximum hotspot should not exceed 115% in any case.
- g. For purposes of dose planning and calculation of monitor units for actual treatment, this protocol requires tissue density heterogeneity corrections approved by IROC. Examples of appropriate tissue density heterogeneity correction algorithms include properly commissioned superposition/convolution (collapsed cone), AAA, and Monte Carlo. Simple pencil beam and Clarkson algorithms that account for attenuation but not scatter will not be allowed.
- h. For 3D conformal cases, coplanar or non-coplanar beam arrangements will be custom designed for each case to deliver conformal prescription dose distributions.
- i. For IMRT cases, the treatment dose plan may be made up of multiple static beams or arcs, and the apertures are determined by inverse treatment planning

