- If after start of IV methylprednisolone at 2 to 4 mg/kg/day there is no improvement within 3 to 5 days, consider start of immunosuppressive therapy such as TNF inhibitors (e.g., infliximab at 5 mg/kg every 2 weeks). Caution: It is important to rule out sepsis and refer to infliximab label for general guidance before using infliximab.
- Consider whether patient may require IV IG, plasmapheresis.
- Once the patient is improving, gradually taper steroids over ≥ 28 days and consider prophylactic antibiotics, antifungals, or anti-PJP treatment (refer to current NCCN guidelines for

Additional Information:

- ❖ If drugs are given and then patient develops AE before or during radiation, radiation is also held, stopped, unless the treatment field is clearly unrelated to the AE (e.g. liver radiation in a patient who develops pneumonitis), provided the patient is clinically stable for radiation treatment.
- ❖ If either drugs are held then radiation is also held. If all radiation has not been delivered as per protocol, radiation would resume the week following the next drug administration, do not skip.
- ❖ If drugs are held, then any remaining radiation is also held until a week after the next cycle begins, per protocol.
- ❖ If patient experiences an AE, requiring drug hold/discontinuation, both drugs will be held.
- ❖ If drug or radiation is permanently discontinued for toxicity before completion of protocol treatment, the subject would need to come off treatment.

Infusion-Related Reactions		Dose Modifications	Toxicity Management
Severity Grade Any Grade			
 - Management per institutional standard at the discretion of investigator - Monitor patients for signs and symptoms of infusion-related reactions (e.g., fever and/or shaking chills, flushing and/or itching, alterations in heart rate and blood pressure, dyspnea or chest discomfort, skin rashes etc.) and anaphylaxis (e.g., generalized urticaria, angioedema, wheezing, hypotension, tachycardia, etc.)
Grade 1	The infusion rate of study drug/study regimen may be decreased by 50% or temporarily interrupted until resolution of the event		For Grade 1 or Grade 2: 
 - Acetaminophen and/or antihistamines may be administered per institutional standard at the discretion of the investigator - Consider premedication per institutional standard prior to subsequent doses - Steroids should not be used for routine premedication of Grade ≤ 2 infusion reactions.

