10. STUDY CALENDAR

Baseline evaluations are to be conducted within 4 weeks prior to start of protocol therapy. Scans and x-rays must be done ≤5 weeks prior to the start of therapy. In the event that the patient’s condition is deteriorating, laboratory evaluations should be repeated within 48 hours prior to initiation of the next cycle of therapy. Note that all study visits in the calendar are specified by week, but should be performed on the same day of the week when feasible and every effort should be made to schedule them +/-2 days.

Cohort 1 – Non small cell lung cancer

	Pre- Study	Wk 1	Wk 2	Wk 3	Wk 4	Wk 5	Wk 6	Wk 7	Wk 8	Wk 9	Wk 10	Wk 11	Wk 12	Wk 13- 52	Off Treatment ^e
MEDI4736(durvalumab)		A				A				A				A ^e	
Tremelimumab		B				B				B				B ^e	
Radiation therapy			C				C				C			C ^e	
Informed consent	X														
Demographics	X														
AE/SAE Assessments ^m		X				X				X				X ^e	X
Medical history	X	X				X				X				X ^e	
Concurrent meds ^d	X													X	X
Physical exam	X	X				X				X				X ^e	X
Vital signs ^p	X	X				X				X				X ^e	X
Performance status	X	X				X				X				X ^e	X
CBC w/diff, plts	X	X ^k				X				X				X ^e	X
Serum chemistry ^a	X	X ^k				X				X				X ^e	X
EKG ^j	X														
Hepatitis B and C and HIV ⁿ	X														
Urinalysis	X ⁱ														
Tumor measurements	X		Tumor measurements should be performed during week 7 or 8 and then repeated every 12 weeks +/- 5 days. Documentation (radiologic) must be provided for patients removed from study for progressive disease.												
Radiologic evaluation ^l	X		Radiologic measurements should be performed during week 7 or 8 and then every 12 weeks +/- 5 days while on treatment .												X ^o
B-HCG	X ^b	X				X				X				X ^e	X ^e
Head MRI ^{dh}	X													X ^d	
Research blood samples	X					X									
Biopsy of site(s) of disease	X ^f							X ^g							
PRO-CTCAEⁿ	X		X		X		X		X				X	X	X

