13.6 Interim Safety Analysis

NSCLC: For an early and detailed safety assessment, complete review of the adverse event data for the first 10 patients assigned to MEDI4736(durvalumab)/tremelimumab/high-dose RT and for the first 10 patients assigned to treatment with MEDI4736(durvalumab)/tremelimumab/low-dose RT will occur after completion of one cycle (4 weeks) of therapy. If three or more patients within a therapy arm experience one or more dose-limiting toxicities, the addition of RT will be considered too toxic and enrollment to that arm will stop.

Colorectal Cancer: Concurrent with the end of the first stage of each Simon design, a complete safety review of adverse event data will be conducted for each treatment after completion of two cycles of therapy. If three or more patients within a therapy experience one or more severe or pre-specified dose-limiting toxicities, enrollment to that arm will stop.

The table below summarizes the probability of observing three or more severe or unexpected toxicities in the first 10 patients of a cohort for various underlying true probabilities. If the true incidence of severe or unexpected toxicities is 25% or higher, then the probability is at least 0.47 that three or more patients will be observed with these toxicities at the time of the early safety monitoring.

True Incidence of Unexpected or Severe Toxicity	Probability of Observing Three or More Patients with Toxicity among First 10
10%	0.07
15%	0.18
20%	0.33
25%	0.47
30%	0.62

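### Section 5.2 counts DLTs toward the 3-of-10 arm-stopping rule only in days 1-28, so cycle-2 events cannot count, and Sections 5.2 and 13.6 disagree on when to review and what to count

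*Combined protocol and SAP*

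**What the plan says.** **The rule.** Section 5.2 applies it to the first 10 NSCLC patients assigned to each RT arm: "If three or more patients within a therapy arm experience one or more pre-specified dose-limiting toxicities", RT is judged too toxic and enrolment to that arm stops. The colorectal arms have a matching rule at the end of Simon stage 1.

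**The window.** In Section 5.2, "the DLT period in this study refers to toxicities experienced during the first 4 weeks of treatment". Monitoring continues afterwards, but a DLT is defined as a toxicity within the evaluation period.

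**Review time.** For NSCLC, Section 5.2 says the review "will occur after completion of two cycles of therapy". Section 13.6 puts the same review after one cycle, which it equates with 4 weeks. For colorectal, Section 13.6 reviews after two cycles.

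**Counted event.** For colorectal, Section 5.2 counts pre-specified DLTs only. Section 13.6 counts severe toxicities as well.

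**RT timing (Section 5.1).** Both arms start in week 2. Arm B repeats its course "with each of the first 4 cycles of treatment (weeks 2, 6, 10, 14". Arm A gets three fractions, never on consecutive days, and "The total treatment time must not extend over more than 10 calendar days".

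**Laboratory schedule (Section 10).** In both calendars the row "CBC w/diff, plts" and the chemistry row are marked at week 1, week 5 and week 9, with nothing in weeks 2-4.

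**Operating characteristics.** Section 13.6 tabulates the chance of three or more affected patients in 10 and says "If the true incidence of severe or unexpected toxicities is 25% or higher, then the probability is at least 0.47". It gives no period for that incidence.

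**The concern.** The early rule is there to show whether adding RT to the two antibodies is too toxic. Section 5.2 itself calls the combination relatively untested. It is the only numerical rule in the plan that closes an RT arm for toxicity.

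Under Section 5.2, a Grade 3 or higher event in weeks 5-8 would be seen at the two-cycle NSCLC review but could not be counted as a DLT. Under Section 13.6, the NSCLC review might take place before that event happened. Sites and the study team could apply different rules to the same data. The probabilities in 13.6 could also be read as the chance of catching toxicity over a longer exposure than the one counted.

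**Working it through.** **1. The plan's own table.** Inputs are n = 10 and a threshold of 3 (Sections 5.2 and 13.6).

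P(X ≥ 3) = 1 − (1−p)^10 − 10p(1−p)^9 − 45p²(1−p)^8

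| True incidence p | Section 13.6 | Exact |
|---|---|---|
| 10% | 0.07 | 0.070 |
| 15% | 0.18 | 0.180 |
| 20% | 0.33 | 0.322 |
| 25% | 0.47 | 0.474 |
| 30% | 0.62 | 0.617 |

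The table reproduces, except that the 20% row should read 0.32: 1 − 0.1074 − 0.2684 − 0.3020 = 0.3222.

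**2. RT inside days 1-28.** Week w covers days 7(w−1)+1 to 7w.
- Arm B: weeks 2, 6, 10 and 14 are days 8-14, 36-42, 64-70 and 92-98. One course of four (2 of 8 Gy) falls inside.
- Arm A, earliest finish: start day 8, fractions on days 8, 10 and 12. This leaves 28 − 12 = 16 days.
- Arm A, latest finish: start day 14 and use 10 calendar days, ending on day 14 + 10 − 1 = 23. This leaves 28 − 23 = 5 days.

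**3. Laboratory data inside the window.** The week 1 draw is pre-treatment, and screening values may replace it. The next is at week 5, nominally day 29. With the ±2-day allowance it falls on days 27-31, so it is sometimes inside the window.

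**4. What the rule detects if some events come later.** Let f be the share of affected patients with a qualifying event by day 28. The documents give no value for f, so it is an assumption shown over a range. The counted incidence is f × p.

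| Two-cycle incidence | f | Counted incidence | P(3 or more of 10) |
|---|---|---|---|
| 30% | 1 | 30% | 0.62 |
| 30% | 2/3 | 20% | 0.32 |
| 30% | 1/2 | 15% | 0.18 |
| 30% | 1/3 | 10% | 0.07 |

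The 13.6 figures therefore describe the DLT count only when the stated incidence is the 4-week incidence.

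**5. A two-cycle window (day 56).** It would contain two of Arm B's four courses, and 56 − 23 = 33 to 56 − 12 = 44 days after Arm A's course.

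**The case against.** A one-cycle DLT window is a legitimate design choice. All of Arm A's radiation and Arm B's first course fall inside it on normal timing. Section 5.2 calls for a complete review of adverse event data, not only a DLT count. The severe-toxicity limb of the colorectal rule in 13.6 is not tied to 4 weeks. Section 13.8.1 pauses a regimen if 33% or more have severe toxicity at any time after the early review. All of this stands, and it limits the point. The pause covers the gap only in part: it pauses rather than stops, begins after the early review, and is expressed per cohort, so its denominator is unclear. Three of 10 (30%) would not reach it.

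Three stronger readings are tempting, and the documents do not support them.
- *The rule is blind to most of the toxicity.* No onset-time distribution is given, so the loss depends entirely on f.
- *There are no labs in the window.* The day 1 draw is nominally inside, week 5 labs may fall on days 27-28, and unscheduled findings and clinical events in days 1-28 count.
- *Patients whose RT is deferred dilute the count.* Section 6 says "If drugs are held, then any remaining radiation is also held until a week after the next cycle begins, per protocol", so a patient can be among the 10 with no RT in the window. Recomputing at 25% with 9 or 8 patients gives 0.40 or 0.32, but that assigns the unirradiated patients zero risk. They received both drugs, and any qualifying Grade 3 or higher event counts. Section 5.2 also counts patients who interrupt for toxicity meeting those criteria. The figures are a floor, not an estimate.

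**Conclusion.** The point holds as a mismatch within the plan. Under Section 5.2 the arm-stopping count excludes any toxicity first arising after day 28, although the NSCLC review in that section collects cycle-2 events. Sections 5.2 and 13.6 disagree on NSCLC review time and on the colorectal counted event. The 13.6 table uses another event label (severe or unexpected toxicity) and states no period.

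The timing facts come directly from the documents. The fall in detection from 0.62 to between 0.32 and 0.07 is illustrative: it assumes 30% two-cycle incidence and f between two-thirds and one-third. The 20% row is a rounding-level error.

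**What to change.** - Reconcile Sections 5.2 and 13.6 so that review time, counted event and counting window agree for each cohort. The two-cycle review point already in 5.2 (NSCLC) and 13.6 (colorectal) would let cycle-2 events count, using data already collected at weeks 5 and 9.
- State in the 13.6 table which event and period its incidence refers to, recompute the probabilities for that period, and correct the 20% row to 0.32.
- Keep every treated patient assigned to the RT arm in the count, and report how many received RT within the window. Requiring at least one RT fraction would drop patients too ill from the drugs to reach RT.

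**Cost.** The change is to protocol wording and needs no new data. Where 13.6 would have reviewed NSCLC after one cycle, the review comes about 4 weeks later. At the projected 6 NSCLC patients a month over three arms (6 / 3 = 2), that is about two more patients per arm if accrual is not held. An unchanged 3-of-10 threshold over a longer window also stops an arm more often, including for background drug toxicity. For example, if the counted incidence rose from 10% to 15% (assumed), the stopping probability would rise from 0.07 to 0.18. A two-cycle window still leaves out two of Arm B's four courses. The 33% pause in 13.8.1 must cover those, so its denominator should be made explicit.
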